### 4.3 Dose Escalation Rules

The Dose Escalation Phase of this trial will proceed using a conventional 3 + 3 + 3 approach.

If 0 of the first 3 patients treated at a given dose level experience a drug-related DLT during the DLT evaluation period, the dose will be escalated, and 3 patients will be enrolled and treated at the next higher dose level (up to the planned highest dose level).

If 1 of the first 3 patients treated at a given dose level experiences a drug-related DLT, then 3 additional patients will be enrolled at that dose level (thus making a total of 6 patients in this cohort) to further assess the safety of the combination of MGD007 and MGA012.

- If  $\geq 2$  of these 3 additional patients (i.e.,  $\geq 3$  of the 6 patients enrolled in the cohort) experience a DLT, it will be concluded that the MTD has been exceeded, and 3 patients will be enrolled and treated at the next lower dose level.
- If 1 of these 3 additional patients experiences a drug-related DLT, then another 3 additional patients (for a total of 9 patients in the cohort, 3 + 3 + 3) will be enrolled and treated at that dose level to further characterize the safety of MGD007.

- If 0 of the 3 additional patients experiences a DLT, then the dose will be escalated, and 3 patients will be enrolled at the next higher dose level.

If  $\geq 2$  patients out of the first 3 patients treated at a given dose level, or  $\geq 3$  of first 6 patients treated at a given dose level, or  $\geq 3$  out of 9 patients treated at a given dose level experience a drug-related DLT, then it will be concluded that the MTD for MGD007 has been exceeded at that dose level, and an additional 3 patients will be added and treated at the next lower dose level.

Following these rules for dose escalation, the MTD/MAD will be the highest dose administered during the Dose Escalation Phase of the study at which the incidence of DLT is  $< 33\%$ . Depending on the nature of the DLT, the dose reduction can concern both drugs or only one.

Dose escalation to the next dose level is permitted only after the patients enrolled in the current dose cohort have completed the DLT evaluation period and safety data have been reviewed by the Sponsor's Medical Monitor and Pharmacovigilance Physician as well as the Investigators participating in the study.

At the discretion of the Sponsor, dose escalation may be stopped before an MTD is reached. In this case, the MAD may be chosen based on an assessment of available PK, PD, safety, and response data. An MTD does not have to be reached to initiate the Cohort Expansion Phase of the study if the available data demonstrate that a lower dose level may provide antitumor activity while minimizing potential risk. In addition, if an MTD is established, the Sponsor may decide to open the Cohort Expansion Phase at a dose lower than the MTD, based on the totality of the PK, PD, biomarker, safety, and response data.

At the discretion of the Sponsor, any escalation cohort at a dose level not exceeding the MTD may be expanded to a maximum of 15 patients for further evaluation of safety, PK, and antitumor activity.

When an MTD or MAD is established, any patient remaining on treatment at a lower dose level will be given the option to escalate to the MTD/MAD dose.

#### **4.4 Guidelines for Dose Modification**

No dose modifications will be allowed with exception of 1) reduction of infusion rate during re-challenge for patients experiencing an infusion reaction ([Section 7.2](#)) or 2) reduction of dose in patients receiving MGD007 or MGA012 at a dose that is subsequently determined to exceed the MTD ([Section 4.1.1](#)).

##### **4.4.1 Dose Delays in Escalation and Expansion Cohorts**

Patients who experience toxicity that is potentially dose-limiting should have study drug held pending assessment, management, and resolution of the toxicity. For patients in whom the toxicity is assessed to be unrelated to study drug or for whom the toxicity does not meet the

criteria for DLT, therapy may be re-instituted at the same dose and schedule that was administered prior to the event, presuming the toxicity has resolved as per guidelines outlined in [Section 7](#). Dose interruptions of up to 28 days are allowed. Reinstitution of therapy shall be conducted as follows:

- The procedures at the originally scheduled missed visit should be performed as soon as possible with treatment reinstated as if no delay had occurred, picking up at the day where the interruption occurred, and patients should receive the planned dose and have assessments performed as outlined in the Time and Events Schedule ([Appendix 1](#)).

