## 4 STUDY DESIGN

### 4.1 Overall Study Design and Plan

[figure not shown]
This study is an open-label, Phase 1b/2 dose escalation and cohort expansion study designed to characterize the safety, tolerability, PK, pharmacodynamics, immunogenicity, and preliminary antitumor activity of MGD007 and MGA012, administered in combination by IV infusion, in patients with histologically proven, relapsed/refractory metastatic colorectal carcinoma, irrespective of the KRAS and MMR status of their tumors. This study will enroll patients as described below.

The study will proceed in 2 distinct phases as follows: Dose Escalation Phase to determine the MTD or MAD (if no MTD is defined) of the combination, followed by a Cohort Expansion Phase to further define the safety and initial antitumor activity of the combination with the doses established in the Dose Escalation Phase.

Patients will be treated with MGD007 and MGA012 as shown in [Figure 11](#). MGD007 will be administered at the target dose for each assigned cohort as an IV infusion over 120 minutes, once weekly (QW), in 8-week treatment cycles. MGA012 will be administered at 3 mg/kg as an IV infusion over 60 minutes, once every 2 weeks (Q2W) beginning on Cycle 1 Day 15, and every 2 weeks thereafter. For each patient, administration of the first dose of MGA012 will occur 2 weeks after the first dosing of MGD007. The DLT evaluation period will last until Cycle 1 Day 42. Disease status will be evaluated on Cycle 1 Day 56 ( $\pm$  3 days) using CT and/or MRI as appropriate for the sites of disease, accompanied by physical examination, and will then be evaluated every 8 weeks while on study treatment. Although response assessment will be performed according to both conventional (RECIST 1.1 [\[Appendix 5\]](#)) and irRECIST ([Appendix 6](#)), patients will be managed according to irRECIST principles. This approach allows for limited treatment of patients beyond the initial radiographic documentation of disease progression, assuming that the Investigator feels that the patients are tolerating therapy adequately, that patients remain otherwise clinically stable despite this initial radiographic evidence of disease progression, and that the Investigator feels the patient may still derive benefit from continuation of therapy.

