## **9.9 Radiographic, CT, or MRI Assessments**

Baseline tumor imaging consists of a CT/MRI scan for all patients. The subsequent tumor assessments on treatment should use the same imaging modality as that for the baseline assessment; for subsequent imaging timepoints see [Appendix 1](#).

A CT or MRI scan of the brain will be performed in cases in which it is clinically indicated (e.g., suspicion of brain metastases) and repeat brain scans will be performed only if the screening brain scan was positive, or as clinically indicated.

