## 11 ASSESSMENT OF EFFICACY

### 11.1 Efficacy Assessments

#### 11.1.1 Disease Response Assessments

Tumor assessments will be obtained using CT and/or MRI scans. Target and non-target lesions will be designated at screening and then evaluated at Cycle 1 Day 56 ( $\pm 3$  days), and then every 8 weeks while on study treatment. At each tumor assessment time point, the overall response status will be determined based on assessment of target and non-target lesions as well as appearance of any new lesions. For patients who discontinued from study treatment due to reasons other than documented, confirmed progressive disease, their treating physicians will be contacted every 3 months during post-treatment follow up period about the response status and survival of these patients.

For RECIST v1.1 ([Appendix 5](#)), the overall responses will be categorized as Complete Response (CR), Partial Response (PR), Stable Disease (SD), Progressive Disease (PD), or Not Evaluable (NE). For patients who experience an objective response of CR or PR, responses will be considered unconfirmed until the response has been documented by a subsequent confirmatory scan obtained no less than 4 weeks after the initial scan demonstrating an objective response.

For irRECIST ([Appendix 6](#)), the overall responses will be categorized as immune-related Complete Response (irCR), immune-related Partial Response (irPR), immune-related Stable Disease (irSD), immune-related Progressive Disease (irPD), or immune-related Not Evaluable (irNE). For patients who experience an objective response of irCR or irPR, responses will be considered unconfirmed until the response has been documented by a subsequent confirmatory scan obtained no less than 4 weeks after the initial scan demonstrating an objective response.

For the purpose of patient management, the response determination according to irRECIST will prevail.

For patients who demonstrate acceptable tolerability of treatment with MGD007 and MGA012, and an objective response assessment of irCR, irPR, or irSD, or unconfirmed clinically stable irPD, therapy may be continued.

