### 14.6.3 Time-to-event Endpoints and Analyses

Progression-free survival will be defined as the time from the first dose date of MGD007 to the date of first documented progression or death from any cause, whichever occurs first. The documented progression is determined by objective assessment of disease per RECIST v1.1 and irRECIST, respectively. For patients who are not known to be dead or progressed at the time of data cut-off for PFS analysis, the PFS will be censored at the date of the last tumor assessment. Specifically, the following censoring rules will be applied as primary analysis of PFS. Sensitivity analyses may be performed to assess the robustness of the primary PFS analysis and will be described in the SAP.

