EVALUATION/ PROCEDURE	Screening 	Cycle 1							Cycle 2 and Subsequent Cycles						EOTV 	Post-treatment Follow up 
		Day 1	Day 2 	Day 8 (± 1day)	Day 15, 29, 43 (± 1day)	Day 16,17, 19 	Day 22, 36, 50 (± 1day)	Day 42 (± 5 days)	Day 56 (± 3 days)	Day 1 (± 1day)	Day 2 	Day 8 (± 1day)	Day 15, 29, 43 (± 1day)	Day 22, 36, 50 (± 1day)		
See Appendix 2 for list of endocrine tests; To be taken pre-infusion. Labs can be taken up to 3 days before infusion.																
CEA	X								X							X
CEA: At screening; Cycle 2, Day 1 pre-dose; Day 1 of every other cycle thereafter - predose																
Urinalysis	X	X							X							X
See Appendix 2 for list of urinalysis test; To be taken pre-infusion. Labs can be taken up to 3 days before infusion.																
Pharmacokinetic, Immunogenicity, and Pharmacodynamic Biomarkers	Sampling to be performed according to Appendix 3 .															
Tumor biopsies on study (Cohort Expansion subjects only)	X							X								
On treatment tumor biopsy: Fresh tumor biopsy pre-treatment (after enrollment and prior to the Cycle 1 Day 1 dose) and at Cycle 1 Day 42 ± 5 days. Paired tumor biopsies will be mandatory if tumor lesions are accessible for biopsy with acceptable clinical risk in the judgment of the investigator and after discussion with the sponsor.																
Tumor Assessment (CT/MRI)								X						X	X	
Tumor Assessment (CT/MRI): Radiographic disease assessments will occur on Cycle 1 Day 56 (±3 days) and then every 8 weeks. Assessment will also be done at End of Treatment Visit.																
KRAS and MMR	X															
Formal documentation required for all patients in the Cohort Expansion Phase. Should be captured as part of cancer disease history. If unavailable during screening, this can be collected while on study.																
Follow-up by phone or electronic contact	Overall Survival Follow-up: Documentation of overall survival follow-up described in protocol Section 9.12 .															X

- 1 The Screening visit should occur within 28 days prior to Day 1.
  - 2 The End of Treatment Visit should be performed after the patient has met off-treatment criteria and occur no later than 30 days since the last study dose and before any subsequent anti-cancer treatment; see [Section 9.11](#).

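### A Cycle 1 dose hold delays both tumor scans that feed the 16-week PFS rate, so this descriptive primary measure can read high; scans should be timed by calendar from first dose

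*Protocol*

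**What the plan says.** Protocol 4.1 gives MGD007 "once weekly (QW), in 8-week treatment cycles". In 4.4.1, "Dose interruptions of up to 28 days are allowed"; on resumption the rule is "treatment reinstated as if no delay had occurred, picking up at the day where the interruption occurred", and the patient should "have assessments performed as outlined in the Time and Events Schedule", which is Appendix 1. Section 9.9 also sends the reader to Appendix 1 for imaging times.

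Appendix 1 states: "Radiographic disease assessments will occur on Cycle 1 Day 56 (±3 days) and then every 8 weeks". Its grid has a Day 56 column for Cycle 1 and another for Cycle 2 onward. Section 11.1.1 likewise sets the first scan by cycle day, "and then every 8 weeks while on study treatment", without saying whether the 8 weeks run on the calendar or in cycle days.

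The endpoint uses a different clock. Protocol 14.6.3 says "Progression-free survival will be defined as the time from the first dose date of MGD007", and SAP 5.1.2 does the same for PFS and irPFS. Protocol 3.2.1 names the 16-week PFS rate, with objective response and disease control, as a primary expansion measure. Protocol 14.6.1 takes it at 16 weeks from first dose; 14.6.3 and SAP 6.6.2.1 read it at 4 months and equate the two.

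Section 7 describes resumption differently. For transaminases, pneumonitis, skin reactions and nephritis (7.5.1.1, 7.5.3 to 7.5.5), treatment restarts at the next dose on the schedule, and 7.5.1.1 also counts missed doses.

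**The concern.** During a hold the cycle clock stops and the PFS clock does not. Progression is dated when it is documented, so a patient scanned late is dated late. Scan 2 is due on Day 112, the 16-week point itself, and a delay can carry it past the landmark. A patient who progressed between the two scans then counts as progression-free at 16 weeks.

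Holds are an expected part of this plan. Section 7 holds both drugs for several toxicities with resumption allowed, and 8.1.1 allows an interruption of up to 4 weeks for palliative radiotherapy. Scan timing would therefore vary with tolerability.

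Nothing planned corrects for this. The censoring table (Protocol Table 14, SAP Table 2) covers two or more missed scans, not late ones. The optional sensitivity analysis in SAP 6.6.2.1 counts progression or death whenever it occurs, but keeps the late date.

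**Working it through.** **The plan's own figures.** There is no planning value for the 16-week PFS rate. The only precision figures are the exact intervals in Protocol Table 13. All six rows reproduce by Clopper-Pearson; for example, 7/25 = 28% gives 12.1% to 49.4%. One patient in 25 is 4 points.

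**Landmark.** 16 weeks = 112 days. SAP 5.1.2 divides (date − first dose + 1) by 365.25/12 = 30.4375, so 4 months = 4 × 30.4375 = 121.75 days. Day 112 is 112/30.4375 = 3.68 months.

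**Scan days after a Cycle 1 hold of d days.** Scan 1 is at 56 + d. Scan 2 is at 112 + d, whether the next 8 weeks are counted by calendar or by cycle.

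| Hold | Scan 1 | Scan 2 | In time at 112 | In time at 121.75 |
|---|---|---|---|---|
| none | 56 | 112 | yes | yes |
| 7 days | 63 | 119 | no | yes |
| 14 days | 70 | 126 | no | no |
| 28 days | 84 | 140 | no | no |

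At 121.75 days, a nominal scan 2 is in time for a 9-day hold (Day 121) and late for a 10-day hold (Day 122). At 112 days, any hold over 3 days makes scan 2 late even at the early edge of its window (109 + d > 112).

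**Cycle 2 holds.** Under the Day 56 column, scan 2 moves. Under a calendar reading of 8 weeks from scan 1, it does not. The text does not decide.

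**Size, for illustration.** Assumptions: exponential progression; median 2.0 months = 60.875 days, borrowed from the third-line figures in Protocol 2.2; progression found only at scans; a share f of patients held, which the documents do not give.

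- S(t) = 0.5^(t/60.875): S(56) = 52.9%, S(70) = 45.1%, S(84) = 38.4%, S(112) = 27.9%.
- If scan 2 is late, a held patient counts as progression-free with probability S(day of scan 1).
- Estimated rate = (1 − f) × S(112) + f × S(day of scan 1).

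With f = 30%:

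- On schedule: 27.9%.
- 14-day Cycle 1 hold: 0.7 × 27.9 + 0.3 × 45.1 = 33.1%, a shift of 5.1 points from unrounded values (about 1.3 patients in 25).
- 28-day Cycle 1 hold: 0.7 × 27.9 + 0.3 × 38.4 = 31.1%, a shift of 3.1 points.
- Scan 1 on time, scan 2 late: 0.7 × 27.9 + 0.3 × 52.9 = 35.4%, a shift of 7.5 points. This is the upper bound.

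These results are the same at either landmark, because scan 2 is late at both. A 7-day hold differs. At 121.75 days its scan 2 (Day 119) is in time, and the shift is between −0.6 and +0.4 points depending on how the scan window is treated.

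**Range.** For a 14- or 28-day Cycle 1 hold, or scan 2 alone late, the shift is 1.0 to 2.5 points at f = 10% and 5.2 to 12.5 at f = 50%. At f = 30% with medians from 1.7 to 4.0 months, it is 4.3 to 5.1 points (14-day), 2.7 to 3.1 (28-day) and 6.0 to 7.5 (scan 2 only). If 20% of events are deaths dated exactly, the 14- and 28-day shifts fall to 4.1 and 2.5 points.

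**The case against.** **The stopped clock is one reading.** Section 7's resumption wording suggests a schedule that keeps running, in which case scans would not move. Section 4.4.1 also asks for procedures from a missed visit to be done as soon as possible, which could cover a scan falling inside a hold. This stands as a reason to reconcile the sections. It does not remove the problem: 4.4.1 is the general rule for delays, it ties later assessments to the resumed day, and nothing in either document keeps scans on the calendar.

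**A reader might infer that any hold beyond 3 days biases the result.** That is true only at a strict 112-day landmark; the 4-month reading absorbs holds up to about 9 days. At a strict Day 112 the ±3-day window is itself a distortion. With uniform timing, 3/7 of on-time scans fall on Days 113 to 115, giving about 38.9% with no holds at all. Against that baseline, holds add only about 0 to 4 points at 30% held.

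**A reader might infer that the patients who tolerate treatment worst look progression-free longest.** The documents do not show this. Under 5.4, a drug-related DLT or a drug-related delay over 28 days is a criterion for stopping treatment (with case-by-case exceptions), and the End of Treatment Visit includes a scan, although that visit is optional.

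**A reader might infer that duration of response is inflated too.** This is not established. A hold before response delays the start of the duration as well as its end.

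**The study is descriptive.** SAP 6.1 says so in substance, and the PFS rate has no null value, test or threshold. This stands: no type I error is at stake.

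**Conclusion.** The point holds in a limited form. A Cycle 1 hold moves scans 1 and 2 while PFS stays on the calendar. For Cycle 2 holds the text is ambiguous. The 16-week PFS and irPFS rates can be biased upward, by holds of about 10 days or more at the 4-month landmark and by holds over 3 days at a strict 112-day landmark. Under the assumptions above, with 30% held, the illustrative shift is about 3 to 5 points for Cycle 1 holds of 14 to 28 days, with an upper bound of 7.5. Exactly dated deaths make it smaller. The true size cannot be determined from the documents, which give neither a hold frequency nor a planning PFS rate. A shift of this size is under two patients in 25 and small beside the sampling uncertainty, but it is systematic and falls on a primary expansion measure. Severity: should-fix, as a cheap improvement.

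**What to change.** - **Protocol 4.4.1, 11.1.1 and Appendix 1:** state that tumor assessments are timed by calendar from the first MGD007 dose (Day 56, Day 112, then every 56 days, each ±3 days) and are not moved by dose holds. Limit the resume-where-interrupted rule to dosing and dose-linked procedures.
- **Protocol 4.4.1 and Section 7:** reconcile the two descriptions of how treatment resumes. Which dosing rule applies is for the sponsor and investigators to settle; the scan rule should hold under either.
- **SAP 6.6.2.1, with Protocol 14.6.1 and 14.6.3:** name one landmark that falls after the scan 2 window closes on Day 115. The 121.75-day reading does; a strict Day 112 reading does not.

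**Cost:** a sentence in each protocol section, a footnote in Appendix 1 and one landmark definition. No scans are added. The downside is that a scan may not coincide with a dosing visit. The scan rule has to be in place before the scans are taken, because a scan not done on time cannot be recovered in analysis.

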## 4.5 Study Duration

Enrollment of the study should last approximately 18 months.

The maximum amount of time an individual patient may be on study is 12 treatment cycles, or approximately 2 years. The total time for conduct of the trial is expected to be approximately 66 months (which includes 2 years of survival follow-up). These estimates of the timing for study conduct may vary from that observed in the actual conduct of the trial.

### 4.5.1 Patient Accrual

The number of patients enrolled in the Dose Escalation Phase cannot be precisely determined in advance. There may be up to 27 patients enrolled depending on results in the course of the trial and the number of MGD007 and MGA012 doses explored. This patient number does not take into account replacement of non-evaluable patients or enrollment to a dose cohort that is expanded in Dose Escalation Phase.

The Cohort Expansion Phase of the study will enroll approximately 25 patients. This number may be higher because at the end of the Cohort Expansion Phase, 15 tumor paired biopsies will be required, if metastases are accessible and obtained with acceptable clinical risk (see [Section 5.1, # 9](#)). If this number is not reached, additional patients will be enrolled in the study to ensure that the 15 paired biopsies are obtained (see [Section 4.1.2](#)).

The number of patients does not take into account patients who may be replaced for clinical reasons. For initial planning, the number of patients to be enrolled in this trial is anticipated to be approximately 52 patients.

### 4.5.2 Definition of End of Study

The end of study will occur after the last patient has met off-study criteria and the data collection process is completed (time of study database lock).

End of study for each patient is defined as follows: Patient is lost to follow-up (LTFU) ([Section 5.3](#)) or discontinues from the study due to any reason listed in [Section 5.5](#). Each patient's end of study status will be recorded in the End of Study CRF page.

## **4.6           Appropriateness of Measurements**

Routine laboratory evaluations including hematology, chemistry, coagulation, and urinalysis will be carried out in local institutional laboratories. Additional local safety laboratory assessments may be used to supplement the protocol-prescribed assessments and may be used to elucidate certain AEs.

## 5 SELECTION AND WITHDRAWAL OF PATIENTS

To be eligible for study participation, patients must meet all the inclusion criteria. Patients will be excluded from the study if they meet any exclusion criteria. No exceptions to these criteria will be granted by the Sponsor.

The patient population to be enrolled in this study will consist of adult patients with histologically proven, relapsed or refractory metastatic colorectal carcinoma.

